**Table 3: Study procedures**

Event	Screening  (Week -2 to Day 1)	Baseline (Day 1)	Week 1	Week 2	Week 4	Week 8	Early with- drawal
Informed consent	X						
Medical history	X	X		X	X	X	X
Vital signs	X	X		X	X	X	X
Physical examination	X	X		X	X	X	X
Blood & urine collection (safety, efficacy, PK )	X	X		X	X	X	X
ECG	X	X		X	X	X	
Other medications and dietary supplements	X	X			X	X	X
Adverse events		X		X	X	X	X
Functional assessments strength, 6MWT, recumbent graded exercise test, NIRS, PFTs		X			X	X	X
Blood tests: baseline and efficacy		X			X	X	X
Muscle Biopsy Tests: baseline and efficacy		X				X	
Dispense Epicatechin		X		X			

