## 6.2 Withdrawal of Participants

Participants are free to withdraw from the study at any time. Study investigators may elect to withdraw a participant from the study for reasons including an adverse event and inability to comply with study procedures. Reasons for withdrawal of all participants will be recorded for review by the Study Medical Monitor.

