### 6.3.2 Criteria for Dose Reductions

Dose reductions will occur due to adverse drug events and participants will not have their doses re-escalated during the course of the study. Criteria for dose reduction will include:

- Peak (-)-epicatechin PK level >4umol/ml
- Recurrent non-manageable headache
- Increase in baseline safety evaluations >1.5 ULN or 100% change from baseline, excepting CK, AST, ALT
- Abnormal coagulation studies (PT/PTT)
- Other Grade 4 adverse event

If participants require a dose reduction based on the criteria listed above follow the guidelines in Table 4 when reducing a participant's study medication dose.

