**Table 4: Dose reduction schedule.**

Dose Reduction 1	Reduce participant's dose by 50mg/day (25mg AM, 25mg PM dose).
Dose Reduction 2	Withdraw participant from study medication

The Common Terminology Criteria for Adverse Events (CTCAE) published by the Cancer Therapy Evaluation Program will be used to grade adverse events for this trial (See Appendix F).

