### 6.3.3 Study Drug Holiday as Result of Surgical Procedure

If a participant experiences an SAE that necessitates an unanticipated surgical procedure, the study drug should be withdrawn and a "drug holiday" begins. The day the study drug is withdrawn (first day not taking study drug) is Day One of the drug holiday. A drug holiday can last up to 2 weeks (14 calendar days).

Study drug should be withdrawn 2-5 days prior to the scheduled surgery date. The study drug should be restarted 2 days post surgery unless PI has medical rationale for other regimen for restarting study drug.

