## **9 ASSESSMENT OF SAFETY**

### **9.1 Safety Parameters**

Safety parameters for this study will include:

- Review of Systems
- Review of Adverse Events

- Laboratory Assessments: Concurrent with peripheral blood draws listed in the efficacy section and according to the study visit procedure chart, participants will provide blood samples for standard clinical safety testing. Safety panels will include:
  - CBC/Diff
  - PT/PTT
  - CPK
  - Total cholesterol
  - Albumin
  - Total Bilirubin
  - Conjugated Bilirubin
  - GGT
  - ALT/AST
  - Alkaline Phosphatase
  - Sodium
  - Potassium
  - CO2
  - Chloride
  - Calcium
  - BUN
  - Serum Creatinine
  - Serum Glucose
  - Serum Total Protein
  - Fasting lipid profile
  - BNP
- EKG
- Review of Medical History
- Review of Medical and Surgical Events
- Physical and Neurological Exam
- Review of Medication History
- Review of Current Medications and Therapies
- Review of any Adverse Events
- Collection of Vital Signs
- Collection of Height & Weight

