## **9.5 Trial Stopping Rules or Discontinuation Criteria**

Participants may withdraw from the study at any time without prejudice. Study investigators may withdraw participants at any time for reasons such as:

- Inability to comply with study protocol
- SAEs
- Non-tolerable or non-manageable adverse events (AE)
- Severe or sustained unexplained laboratory abnormalities
- Recommendation of suspension of the study by the Medical Monitor

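### A first abnormal PT/PTT or Grade 4 drug event requires only a half dose, and nothing requires the Week 8 PT/PTT result before the open biopsy

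*Combined protocol and SAP*

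**What the plan says.** All references are to the combined protocol and SAP.

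- **Triggers (6.3.2).** The list of reasons to cut the dose includes "Abnormal coagulation studies (PT/PTT" and "Other Grade 4 adverse event". No grade or limit defines an abnormal PT/PTT. The section excepts CK, AST and ALT from its laboratory-increase criterion, but attaches no such exception to the Grade 4 line.
- **Action (Table 4).** Every trigger follows the same two steps. The first cuts the dose by 50 mg/day, to 25 mg morning and evening. Only the second reads "Withdraw participant from study medication". Neither 6.3.2 nor Table 4 contains a hold or a repeat test.
- **Stopping sooner.** Section 6.2: "Study investigators may elect to withdraw a participant from the study for reasons including an adverse event". Section 9.5: "Study investigators may withdraw participants at any time for reasons such as", followed by a list that includes SAEs and unexplained laboratory abnormalities that are severe or persist.
- **The one required hold (6.3.3).** "If a participant experiences an SAE that necessitates an unanticipated surgical procedure, the study drug should be withdrawn".
- **When PT/PTT is measured.** It belongs to the safety panel in 9.1, drawn "Concurrent with peripheral blood draws listed in the efficacy section and according to the study visit procedure chart". In Table 3 the row "Blood & urine collection (safety, efficacy, PK" is marked at screening, Day 1, Weeks 2, 4 and 8, and early withdrawal.
- **Biopsy (8.1, Table 3).** Open biceps biopsies are taken at baseline and at Week 8, after eight weeks of dosing.
- **Risk (10.7.1).** Bleeding is listed as a potential risk, with the statement that nobody has reported what the compound itself does to clotting times.

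**The concern.** A first Grade 4 drug event, or a first abnormal clotting test, is a point at which one would expect drug to be held until the picture is clear. The written rule instead keeps the man on drug at half dose and leaves a stop to judgement. For PT/PTT there is a second gap: the next scheduled test after a Week 4 abnormality falls at the same visit as a planned open muscle biopsy, and nothing puts the result before the incision.

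The stake is first the safety of the individual man. It is also practical. The primary endpoint rests on paired biopsies in ten men, so a biopsy called off on the day with no rule for rescheduling could take 10 pairs to 9.

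**Working it through.** **Inputs.** Starting dose 50 mg twice daily (6.3.1). First reduction 50 mg/day (Table 4). Safety draws on treatment at Weeks 2, 4 and 8 (Table 3, 9.1). Daily dosing for eight weeks, 8 × 7 = 56 days (7.3). Plasma half-life about 2.5 hours at 100 and 200 mg (5.3.3). Visits are taken on their nominal days, since no windows are given.

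**1. The plan's own figure.** 2 × 50 = 100 mg/day; 100 − 50 = 50 mg/day = 25 + 25. Table 4 is reproduced.

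**2. Gaps between scheduled PT/PTT tests.**
- Day 1 to Week 2: 14 days.
- Week 2 to Week 4: 14 days.
- Week 4 to Week 8: 56 − 28 = 28 days.

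**3. Further dosing allowed before the next scheduled test.**
- Week 4 trigger: up to 28 days × 2 = 56 doses of 25 mg, or 1,400 mg; 28/56 = 50% of the treatment period. No scheduled repeat precedes the Week 8 visit.
- Week 2 trigger: up to 14 days × 2 = 28 doses; 14/56 = 25%. The first scheduled repeat is at Week 4.

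Both are maxima and assume the triggering result is acted on at once.

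**4. Required against permitted.**
- Required after a first trigger: half dose (6.3.2, Table 4).
- Required hold: only for unanticipated surgery following an SAE (6.3.3).
- Permitted: withdrawal (6.2, 9.5) and interim outside blood work (6.3.5).
- Expected but untimed: following adverse events to resolution (9.2).
- Notice to the Medical Monitor: 24 hours for SAEs, quarterly summaries for other events (9.3). The monitor also receives safety data through the data system (10.8) and has read access (12.4), but neither section sets an action.
- PT/PTT result before the Week 8 biopsy: not required in any section.

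**5. What a hold and repeat would show.** Two days off drug is 48/2.5 = 19.2 half-lives and seven days is 168/2.5 = 67.2. If any clotting effect follows plasma level, the repeat is an off-drug test. It shows whether the abnormality clears, not whether 50 mg/day is tolerated. A man triggered at Week 4, held for 7 days and restarted at Week 5 would have 56 − 35 = 21 days on drug before the Week 8 test. A hold alone therefore leaves up to about 21 on-drug days untested, which is why one PT/PTT after restart is needed.

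**6. Cost of a 7-day hold.** 7/56 = 12.5% of dosing days.

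**The case against.** The best defence is that Table 4 is a minimum and sits among other safeguards. Section 9.5 names severe or persistent laboratory abnormalities as a reason to withdraw a man. A PT/PTT trigger is an adverse drug event, so 9.2 implies a retest, since the event can hardly be called resolved without one. Section 10.8 provides phone collection of adverse events between visits, which could pick up bleeding symptoms. Men on antiplatelet drugs are excluded (6.1.1, 10.7.1). Section 8.1 refers to standard hospital procedures, which may include pre-operative checks that the protocol does not restate. SAEs already go to the Medical Monitor within 24 hours. Finally, 1.1 says that most drug and metabolites leave plasma by 8 hours, so any effect at biopsy would depend on the last doses rather than on four weeks of them.

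Most of this stands as mitigation, and a careful investigator would probably repeat the test. But none of it requires a hold, dates a retest or puts the Week 8 result before the biopsy. Section 6.3.3 does mention stopping drug 2 to 5 days before surgery. Its opening condition, however, is unanticipated surgery after an SAE, and 8.1 does not apply it to the research biopsy.

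The defence does rule out some stronger readings that a reader might infer:

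- *The protocol keeps a man on drug after a Grade 4 event.* It does not; 6.2 and 9.5 allow withdrawal at any time.
- *Biopsies will be done without a clotting check.* The documents show only that the protocol does not require the result; hospital practice is not visible.
- *28 days and 56 doses measure harm.* They measure permitted exposure. 10.7.1 reports no known effect of the compound on clotting times, and no event rate is given.

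**Conclusion.** The point holds in a limited form. For a first Grade 4 adverse drug event or a first abnormal PT/PTT, the required response is 50 mg/day with drug continued, and anything stronger is discretionary or untimed. After a Week 4 PT/PTT trigger the next scheduled test is up to 28 days later, at the biopsy visit, with no requirement to see the result first. The written rule is less safe than an alternative that costs very little, so it is worth amending.

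The size is per affected man; how many men would be affected cannot be estimated from the documents. The day and dose counts rest on nominal visit days. The off-drug interpretation of a repeat rests on any clotting effect following plasma level. The Grade 4 gap in monitor notice concerns only events that are not SAEs. Confidence is medium, because local practice may already close part of the gap.

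**What to change.** 1. **8.1 and Table 3.** Obtain the already scheduled Week 8 PT/PTT result before the biopsy, on the same day or a few days earlier. If it is abnormal beyond a threshold set by the sponsor and Medical Monitor, repeat it and delay the biopsy within a stated maximum. The investigator and surgeon decide whether to proceed.
2. **6.3.2 and Table 4.** For a first Grade 4 adverse drug event (excepting expected CK, AST and ALT values), or PT/PTT abnormal beyond a set threshold, hold drug until the event resolves or a prompt repeat is normal. About 7 days is suggested for the repeat; the documents give no figure, so the sponsor should confirm it. Then restart at 50 mg/day, with one PT/PTT after restart for men who had the PT/PTT trigger. Otherwise stop drug. The threshold keeps a trivial out-of-range value from forcing a hold.
3. **Optional, 9.3.** Give the Medical Monitor prompt notice of drug-related Grade 4 events that are not SAEs, with the same CK, AST and ALT exception.

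**Cost.** One amendment. Per affected man: one or two extra blood draws, which 6.3.5 allows off site, and up to about 7 of 56 dosing days (12.5%). The Week 8 PT/PTT is at most moved, not added. A delayed biopsy may be taken off drug, which could weaken that man's marker reading but keeps his pair.

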**Table 4: Dose reduction schedule.**

Dose Reduction 1	Reduce participant's dose by 50mg/day (25mg AM, 25mg PM dose).
Dose Reduction 2	Withdraw participant from study medication

The Common Terminology Criteria for Adverse Events (CTCAE) published by the Cancer Therapy Evaluation Program will be used to grade adverse events for this trial (See Appendix F).

### 6.3.3 Study Drug Holiday as Result of Surgical Procedure

If a participant experiences an SAE that necessitates an unanticipated surgical procedure, the study drug should be withdrawn and a "drug holiday" begins. The day the study drug is withdrawn (first day not taking study drug) is Day One of the drug holiday. A drug holiday can last up to 2 weeks (14 calendar days).

Study drug should be withdrawn 2-5 days prior to the scheduled surgery date. The study drug should be restarted 2 days post surgery unless PI has medical rationale for other regimen for restarting study drug.

### 6.3.4 Concomitant Therapy

No new medications may be taken, except over the counter cold remedies, daily multivitamin, and Zantac, during the study period without the agreement of the Study Chair. The exception is any case where such medications are used to prevent injury or disability due to unforeseen adverse events.

### 6.3.5 Patient Care Outside UC Davis

Participants participating in UC Davis studies may not receive protocol therapy at non-UC Davis institutions. However, the following are acceptable:

- For interim blood work done at a non-UC Davis site, a copy of the laboratory slip or other documentation MUST be forwarded to UC Davis for inclusion in the medical record and case report forms.

These guidelines do NOT override any federal, international or sponsoring agency requirements.

Records from any non-UC Davis institutions must be available for audit.

## 7 PHARMACY

### 7.1 Dosing Information and Safety Studies

The safety of this supplement has not been proven in the BMD population. We propose to use a dose at approximately 1.1-1.4 mg/kg/day split between the morning and evening doses. The maximum dose in our population will not exceed 100 mg/day.

#### 7.1.1 Preclinical Rodent Safety Studies

Studies in rodents indicate that (-)-epicatechin can be delivered safely at doses far in excess of the anticipated 1mg/kg dose in human studies. In a study with green tea extracts containing (-)-epicatechin given orally to rats daily for 6 months, the no-observable-adverse-effect level (NOAEL) corresponded to 85 mg (-)-epicatechin/kg [67]. In a developmental toxicity study in pregnant rats using a different tea extract,

the no-observable-adverse-effect level (NOAEL) corresponded to 100 mg (-)-epicatechin/kg (the highest dose tested)[68]. The intraperitoneal (-)-epicatechin median lethal dose (LD50) reported for mice is 1000 mg/kg as stated in the MSDS provided by suppliers such as Sigma-Aldrich. Clarke and Clarke proposed that any substance with an intraperitoneal LD50 of above 1000 mg/kg may be regarded as safe [69].

### 7.1.2 Human Safety Studies

Clinical studies with purified (-)-epicatechin (1-2 mg/kg) in the dose range of Cardero's proposed studies did not reported any adverse events [11, 52]. An extensive literature of human studies using high-flavanol cocoa or chocolate human studies exists, indicating that flavanols could be administered safely at doses up to 1008 mg flavanols per day for 15 days and 444 mg flavanols per day for 6 weeks (reviewed in [8, 9]). A safety study of a green tea extract containing ~110 mg (-)-epicatechin per dose showed that once a day dosing for 4 weeks yielded the same safety profile as placebo, with no significant differences in hemotologic or clinical chemistry [16].

In addition to formal clinical studies, cocoa, chocolate and tea have been used globally on a daily basis for centuries, suggesting that these compounds pose no significant safety risk. Tea is considered a Generally Regarded As Safe (GRAS) compound by the FDA (21 CFR 182.20).

## 7.2 Study Drug Formulation and Procurement

Epicatechin for this study will be obtained from Cardero Therapeutics, Inc. and will be supplied as 25mg clinical trial grade (#3) clear gelcaps in bulk containers. Distribution of medication will be supervised by the UC Davis Investigational Drug Service Pharmacy.

### 7.2.1 (-)-Epicatechin as a Natural Test Substance (Cardero Therapeutics)

(-)-Epicatechin is a naturally-occurring product found in chocolate and tea. It is a member of the flavonoid family. The (-)-epicatechin is purchased commercially and is obtained from tea extracts:

Manufacturer	Sigma-Aldrich
Product #	E1753
Country of Origin:	India

It has >90% purity by HPLC, and has been purified in a GMP facility as follows: it is dissolved in ethanol, treated with charcoal, filtered to remove insolubles, the solvent is exchanged to purified water, and then the solvent is removed by lyophilization.

The final test substance is tested in a GMP analytical lab using appropriate qualified HPLC methods for impurities, including chirality testing. Release specifications require > 90% purity, <5% of the enantiomer, and 5% of catechin. It is also tested for other characteristics typical in GMP materials (identity by 1H NMR, IR; water content by Karl Fischer titration; ethanol content by GC; and the general USP tests of residue on ignition and heavy metals). Based on test results, a Certificate of Analysis is generated (see Appendix) and a %-content by weight is calculated.

Chemical name:	(-)-Epicatechin or (2R, 3R)-2-(3,4-dihydroxyphenyl)chroman-3,5,7-triol
Molecular formula:	C 15 H 14 O 6
CAS #:	490-46-0
Molecular weight:	290.27 grams/mole
Appearance:	off-white to light brown solid
Solubility:	>5 mg/ml in water at 20°C
pKa:	neutral
Taste:	moderately bitter, resembling aspirin in degree of bitterness

(-)-Epicatechin is a single enantiomer containing two defined chiral centers. The structure of (-)-epicatechin is depicted in Figure 1. The absolute stereochemistry of (-)-epicatechin is as shown because it is either isolated from natural sources and further purified, or it is synthesized and compared to the natural isomer.

**Stability** (-)-Epicatechin has been demonstrated to be stable in the lyophilized state for at least six months under refrigeration. A stability study is ongoing and retest dates will be generated based on results.

### 7.2.2 (-)-Epicatechin as supplies as a natural test product

The intended route of administration is oral. (-)-Epicatechin isolated from tea will be supplied by Cardero Therapeutics in gelatin capsules, each containing 25 mg (-)-epicatechin combined with excipients. The test product is used as is, and swallowed with some water. Table 5 describes the (-)-epicatechin capsule formulation.

**Table 5: Contents of the 25mg (-)-epicatechin capsule.**

Component	Role	Amount
Epicatechin	Natural Ingredient	25.00mg
Microcrystalline cellulose® (Avicel PH 102)	Diluent	127.00mg
Crospovidone® (Kollidon CL)	Disintegrant	4.80mg
Citric acid monohydrate®	Acidifying agent	1.60mg
Colloidal Silicon dioxide®	Glidant	0.80mg
Magnesium Stearate®	Lubricant	0.80mg
Total		160.00mg

**Gelatin Capsule** The gelatin has been formulated into hard gelatin capsule shells for use in human pharmaceuticals. The gelatin itself is limed bone gelatin, and has been obtained from Rousselot SAS (production site: [name]). The applicant has obtained Certificate of Suitability No. R1-CEP 2000-029-Rev 03, dated 22 July 2011, from Rousselot. According to this certificate, the substance GELATIN meets the criteria described in the current version of the monograph *Products with risk of transmitting agents of animal spongiform encephalopathies* (no. 1483 of the European Pharmacopoeia).

**Sterility and pyrogen testing** Sterility and pyrogen testing has not been conducted, as test product is supplied as lyophilized powder for oral use only. All products to be included in (-)-epicatechin formulation (capsules) will be USP grade (vitamin C, EDTA, cellulose, lactose). Sterile water will be used to prepare liquid doses for immediate and single use.

**Stability** A stability study of the test product in capsules is ongoing. Retained samples of clinical trial supplies will be tested to confirm potency.

### 7.3 Treatment Cycles Drug Dispensation

Medications will be dispensed for the entire period of time between study visits, and will be clearly marked as investigational drugs per UC Davis Investigational Drug Service Pharmacy procedures. The site will dispense study medication/placebo to the participant and will keep a medication log to document all study medication dispensed to participants. The participant will be instructed to take the study medication per protocol dosing schedule, every day during the eight-week treatment period.

### 7.4 Investigational Product Accounting Procedures

At each study visit, participants will be asked to return used medication containers from the previous month(s), as well as any unused medications. The participating centers will measure any unused medication and the site coordinator will keep records of the participant's medication use.

### 7.5 Maintenance of Randomization Codes and Emergency Unblinding

This study is open-label and no emergency unblinding procedures are necessary.

## 8 ASSESSMENT OF EFFICACY

### 8.1 Laboratory Efficacy Parameters

- Peripheral Blood Tests

Peripheral venous blood will be collected at points specified in the study visit chart to evaluate:

- Creatine phosphokinase (CPK)

- Follistatin
  - mRNA and miRNA biomarker profiles
  - Pharmacokinetics: epicatechin metabolites [serum tested at trough, 2 hours (Tmax), 4 hours after dose at baseline, week 2, week 4 and week 8].
  - Blood lactate testing during exercise: Blood lactate levels will be collected at baseline and 2-minute intervals by finger-stick or ear-stick during 6-minute cycle testing.
- Muscle Biopsy (Biceps Brachii)

Open biopsies of the mid-biceps will be conducted at baseline and after 8 weeks of study medication dosing. The muscle biopsy samples will be collected by open biopsy or according to standard hospital procedures. The minimum amount of muscle tissue required is a small piece of muscle of at least 0.5 x 1.0 x 1.0 cm. If possible, the tissue collected will be of sufficient size to provide 4 (four) pieces of tissue (each 0.5x0.5x0.5cm). Muscle for histological evaluation will be sent fresh to hospital pathology. Muscle tissue for evaluation at outside labs will be immediately frozen in liquid nitrogen-cooled 2-methylbutane and stored at -80°C or -70°C till shipment. Biopsy at baseline will be collected from the lateral aspect of the midpoint of the biceps muscle without the use of depolarizing agents or Bovie catheterization prior to tissue extraction. Biopsy at 8 weeks will be collected from medial aspect of the midpoint of the biceps muscle of the same arm, and must be separated by a margin of at least 1cm to avoid scar tissue from the earlier biopsy.

Histology samples will be evaluated ([name] lab, UC Davis) to examine:

- Fiber size variation
- Tissue necrosis
- Degree of central nucleation
- Presence of basophilic/regenerating fibers
- Fiber type (myosin IHC stains)
- NADH-TR and succinic dehydrogenase (mitochondria)

Muscle biopsy samples will be examined by Western blot ([name] lab, UC San Diego) to evaluate:

Initial Phase (done immediately upon biopsy)

- Muscle regeneration: follistatin, MyoD, myogenin, dystrophin, sarcoglycans, dysferlin
- Oxidation/oxidative stress: SOD1, SOD2, catalase, GSK, nNOS, eNOS
- Mitochondrial function: ETC-I, ETC-V, mitofilin, porin
- Transcriptional regulation: PGC1-alpha
- Collagen deposition: Collagen I, collagen III, fibronectin

Delayed Phase (completed on stored material at a later date if warranted by initial data)

- Glucose transport: Glut1, Glut 4 (and ratio)
- Apoptosis: cytochrome-c, caspase
- Dystrophin-associated complex (DAP) ([name] lab, University of Iowa): sarcoglycans (alpha, beta, gamma, delta, epsilon), laminin-2 (alpha, beta, gamma), alpha dystrobrevin-2, syntrophin
- Matrix metalloproteinase-9

Muscle biopsy samples will be examined by electron microscopy ([name] lab, UC San Diego) to evaluate:

Initial Phase (done immediately upon biopsy)

- Sarcomeric structure
- Mitochondrial number and localization

Delayed Phase (completed on stored material at a later date if warranted by initial data)

- Myofiber volume
- Mitochondrial volume per myofiber volume

- Mitochondrial cristae density

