## 1.2 Study Purpose

This is a proof-of-concept phase 1/2a pilot and endpoint development study that is designed to provide initial evidence of biological activity of (-)-epicatechin. Primary endpoints include initial assessment of tissue-specific evidence of efficacy from muscle biopsy samples. Secondary endpoints include measures of strength and physical function, and safety and adverse event data. Pilot endpoints include assessment of mRNA and miRNA peripheral blood profiles and validation of non-invasive near-infrared spectroscopy (NIRS) muscle perfusion studies during exercise and a recumbent cycle exercise test that may be employed as endpoints in future clinical trials.

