## 1.3 Study Design

This single center open-label pilot study will enroll 10 adults with genetically-confirmed Becker muscular dystrophy, who will receive the purified nutritional extract (-)-epicatechin 100mg/day orally for 8 weeks. After screening visits, participants will be enrolled in the study if they meet all inclusion criteria. They will be evaluated at baseline and at screening, day 1, and weeks 1, 2, 4 and 8. The main criterion for success of the study will be presence of one or more biologic or strength and performance outcome measures (Aims 1 and 2 below) that yield a response magnitude that allows for sufficient power in a Phase II B study with a sample size of 30 individuals.

Evaluations of efficacy will include:

- Assessment of peripheral blood creatine phosphokinase, follistatin, (-)-epicatechin pharmacokinetics, blood lactate during exercise, and baseline and post-treatment mRNA and miRNA biomarker profiles.
- Assessment of baseline and post-treatment muscle biopsy by histology, Western blot, immunostain and electron microscopy.
- Assessment of strength by isokinetic dynamometry and quantitative grip testing, exercise performance during a standardized recumbent cycle test, muscle perfusion of the quadriceps by NIRS during the exercise test, a 6-minute walk test, and body composition by dual-energy x-ray absorptiometry (DEXA).

Evaluations of safety will include comprehensive review of

- vital signs, height and weight
- medical history
- physical and neurological exam
- previous and concomitant medication history
- electrocardiogram
- laboratory safety panels for hematology and coagulation, standard blood chemistries (lipid, hepatic and metabolic profiles)

This is a greater than minimal risk study with prospect for direct benefit. A medical monitor will review safety-related evaluations throughout the duration of the study.

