## 1.4 Specific Aims

**Aim 1. (Efficacy Primary Endpoint): Evaluation of (-)-epicatechin on blood and muscle tissue markers of mitochondrial biogenesis and muscle regeneration in adults with Becker muscular dystrophy.** Treatment with 8 weeks of (-)-epicatechin 100mg daily will induce mitochondrial biogenesis, muscle regeneration, and improved histological appearance in sarcomere morphology.

*Hypothesis:* (-)-Epicatechin will show evidence of mitochondrial biogenesis by Western blot assays of biceps brachii muscle biopsies through increases in ETC1, ETC5 and SOD2 proteins.

*Hypothesis:* (-)-Epicatechin will show evidence of induction of muscle regeneration through increases in PGC1a, decreases in acetylated (inactive) PGC1a, and increases in follistatin,

myogenin, and MyoD compared to pre-treatment baseline as determined by Western blot assays of biceps brachii muscle biopsies.

*Hypothesis:* Administration of (-)- epicatechin will be associated with increases in plasma concentrations of follistatin, a known hormonal regulator of muscle regeneration and a potential pharmacodynamic biomarker.

*Hypothesis:* Administration of (-)- epicatechin will be associated with electron microscopy evidence of increases in mitochondrial number and cristae density within the mitochondria compared to pre-treatment baseline.

*Hypothesis:* Administration of (-)- epicatechin will be associated with increased nNOS expression in skeletal muscle compared to pre-treatment baseline and this increased expression will be associated with improved muscle perfusion during exercise.

**Aim 2 (Efficacy Secondary Endpoints): Evaluation of the effects of (-)-epicatechin on exercise capacity in adults with Becker muscular dystrophy.** Individuals with Becker muscular dystrophy who receive 100mg/day of (-)-epicatechin will demonstrate improved exercise performance and strength that is associated with increases in mitochondrial biogenesis and muscle regeneration.

*Hypothesis:* Using the 6 minute walk test, and a standardized recumbent cycle exercise test with measurement of lactic acid levels, VO2 max, Work max, anaerobic threshold, and NIRS-defined skeletal muscle perfusion (measures of oxyhemoglobin, deoxyhemoglobin, and tissue saturation index) we will detect pre-/post-treatment differences in exercise capacity and endurance that will be clinically significant ( $\geq 5$ -10%) and reflect increases in mitochondrial biogenesis.

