### 6.1.3 Randomization

This is an open-label pilot study, and will not utilize randomization in the study design.

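### Every baseline biopsy is lateral and every Week 8 biopsy is medial, so any difference between the two sites cannot be separated from change on treatment

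*Combined protocol and SAP*

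**What the plan says.** Section 8.1 fixes both sites. For the first: "Biopsy at baseline will be collected from the lateral aspect of the midpoint of the biceps muscle". For the second: "Biopsy at 8 weeks will be collected from medial aspect of the midpoint of the biceps muscle of the same arm". The second specimen "must be separated by a margin of at least 1cm to avoid scar tissue from the earlier biopsy". No alternation or exception is given. The allowance for standard hospital procedures concerns how tissue is taken, not where. Table 3 schedules biopsies only at Baseline and Week 8, with none at early withdrawal.

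The design has no comparison group. Section 1.3: "This single center open-label pilot study will enroll 10 adults". Section 6.1.3: "This is an open-label pilot study, and will not utilize randomization in the study design".

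Section 1.2 gives these specimens the leading role: "Primary endpoints include initial assessment of tissue-specific evidence of efficacy from muscle biopsy samples". Most of the Aim 1 hypotheses in Section 1.4 compare biopsy markers with the pre-treatment specimen. Section 11 calls the study a success if at least one Aim 1 or Aim 2 measure shows a response large enough to power a Phase IIb study of 30. It contains no term for biopsy site, no sensitivity analysis for it and no mention that the site changes.

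**The concern.** Moving the second biopsy to avoid scar is reasonable. The difficulty is that the move goes the same way in all participants. Each change score then contains the change on treatment plus any medial-minus-lateral difference, and no participant supplies the information needed to split the two.

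The output at stake is the size of the biopsy response. A site difference in the expected direction would look like a drug response and could feed an over-optimistic Phase IIb power calculation. One in the opposite direction would hide a real response. Either way it is a bias, so raising the sample size would not shrink it.

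The reach is limited to Western blot, histology and electron microscopy. Plasma follistatin (the Aim 1 hypothesis of "increases in plasma concentrations of follistatin"), CPK and the functional tests do not depend on the biopsy site.

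**Working it through.** The plan gives no power figure or site-difference figure for the biopsy markers, so there is none to reproduce.

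**Inputs from the documents.** n = 10; two biopsies each, lateral then medial (Section 8.1, Table 3); no control group (Sections 1.3 and 6.1.3); significance level 0.05 and a Phase IIb size of 30 (Section 11).

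**Assumptions.** Two-sided testing (sidedness is not stated); one marker at a time; no drug effect; a site shift s of 0.25, 0.5, 0.75 or 1.0 SD of the change score; 80% as the meaning of sufficient power; Phase IIb either paired with 30 or parallel with 15 per group (the design is not stated). Nothing in the documents supports any particular s, and zero is possible.

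**Step 1: can site and time be separated?** Write each change as D = τ + δ + error, where τ is change over the treatment period and δ is medial minus lateral. As planned, all 10 participants have expectation τ + δ. A design matrix with 10 participant effects, time and site over 20 biopsies has 12 columns but rank 11, and the time and site columns are identical (correlation 1.0). With 5 participants in each order the expectations are τ + δ and τ − δ, the rank is 12 of 12 and the correlation is 0. The average of the two order-group means then estimates τ, and half their difference estimates δ.

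**Step 2: significance caused by the shift alone.** The probability of significance in the shift's direction is 1 − F(t₀.₉₇₅,₉; df 9, noncentrality s√10), where F is the noncentral t distribution.

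**Step 3: Phase IIb power implied if the shift is read as response.** Paired: 1 − F(t₀.₉₇₅,₂₉; df 29, s√30). Fifteen per group: 1 − F(t₀.₉₇₅,₂₈; df 28, s√7.5).

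**Step 4: chance that the observed response looks large enough.** The standardized response giving 80% power at 30 is 0.529 SD (paired) or 1.060 SD (15 per group). The chance that the observed mean/SD reaches such a threshold d is 1 − F(d√10; df 9, s√10).

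| Assumed shift (SD) | 0 | 0.25 | 0.5 | 0.75 | 1.0 |
|---|---|---|---|---|---|
| Step 2: significant in shift's direction | 2.5% | 10.6% | 29.3% | 56.2% | 80.3% |
| Step 3: implied power, paired | – | 26% | 75% | 98% | >99% |
| Step 3: implied power, 15 per group | – | 10% | 26% | 51% | 75% |
| Step 4: reaches 0.529 SD | 6.4% | 21.8% | 48.3% | 75.6% | 92.3% |
| Step 4: reaches 1.060 SD | 0.4% | 2.4% | 9.1% | 24.3% | 47.3% |

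Masking follows from the same row. A true change of 1.0 SD has 80.3% power; an opposing shift of 0.5 SD leaves a net 0.5 SD and 29.3%.

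**Step 5: random 5/5 order with an order term** (pooled SD, 8 df, simulated with 200,000 trials per shift for significance and 400,000 for the size thresholds). One-direction rejection is 2.4–2.6% at every shift in the table. The chance of reaching 0.529 SD is 6.6–6.7%, and of reaching 1.060 SD is 0.5%.

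**The case against.** The strongest objection is that the harm is hypothetical. No section reports a lateral-medial difference in any marker, and every percentage above follows from an assumed shift. That stands: the aliasing is certain, its consequence is not. But the plan as written also gives no means of finding out, and it cannot be undone once the biopsies are taken.

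Second, biopsy markers are only one route to success, since blood and functional measures can also meet the Section 11 criterion. Correct. But because one qualifying measure is enough, a single shifted biopsy marker could meet it alone.

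Third, the 6% comparator is per marker. Section 8.1 lists 20 initial-phase Western blot targets. If they were independent, with no shift and no drug effect, the chance that at least one reaches 0.529 SD would be 1 − (1 − 0.0643)^k: about 28% for k = 5, 49% for k = 10 and 74% for k = 20. This multiplicity is separate and counterbalancing does not address it. The table should therefore not be read as the trial-level chance of success.

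Fourth, an uncontrolled study remains confounded with time whatever the biopsy order. True, but that is no reason to keep a second confounder that is easily removed.

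Finally, the histology panel includes fiber typing and the mitochondrial stains NADH-TR and succinic dehydrogenase, which could show whether paired specimens differ in composition. This is a partial check only, because the drug might change the same features.

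**Conclusion.** The concern holds and should be fixed. Biopsy site is completely aliased with time on treatment for endpoints that Section 1.2 makes primary, and no model in Section 11 can separate them. The stated reason for a second site does not require a fixed order.

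The size of the bias is unknown because the shift is unknown. With no shift there is no harm. An assumed 0.5 SD raises per-marker significance in its direction from 2.5% to 29%, and raises the chance of appearing large enough for a paired Phase IIb study of 30 from 6% to 48%. For 15 per group the corresponding rise is from 0.4% to 9%. These figures rest on the assumptions listed with the calculation and apply only to biopsy markers.

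**What to change.** Three short text changes would do it:

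- **Section 8.1:** before the first biopsy, a pre-generated random list assigns 5 participants to lateral at baseline and medial at Week 8, and 5 to the reverse. Both biopsies stay in the same arm, at least 1 cm apart.
- **Section 11:** the model for change in each biopsy marker includes biopsy order, and the estimate of change on treatment is the average of the two order-group means. State as a limitation that time, and any effect of the first biopsy on the same muscle, remain confounded with treatment.
- **Section 6.1.3:** only biopsy order is randomized, not treatment.

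No biopsy, site or staff is added, since both aspects are already sampled in everyone. The cost is one degree of freedom, plus some imbalance if participants drop out. With n₁ and n₂ completers, the effective n is 4/(1/n₁ + 1/n₂) on n₁ + n₂ − 2 df. Power for a true change of 0.996 SD is then:

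| Completers by order | Without order term | With order term |
|---|---|---|
| 5 + 5 | 80.0% | 78.7% |
| 5 + 4 | 74.5% | 72.2% |
| 4 + 4 | 67.7% | 65.3% |
| 5 + 3 | 67.7% | 62.6% |

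With all 10 completing, the effect detectable with 80% power moves from 0.996 to 1.012 SD. The order term removes the bias but measures the site shift itself only roughly: the 95% half-width is t₀.₉₇₅,₈ × √(1/5 + 1/5)/2 = 2.306 × 0.632/2 = 0.73 SD.
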